3.2 Secondary Endpoints

- Among patients requiring supplemental oxygen therapy at the time of enrollment with baseline room air oxygen saturation of $\leq 92\%$, time to cessation of oxygen (O_2) support resulting in stable oxygen saturation (SpO_2) by pulse oximetry. Stable SpO_2 is defined as two consecutive SpO_2 values of $> 92\%$ on room air that are at least 8 hours apart.
- For any patient requiring supplemental oxygen therapy at the time of enrollment (regardless of oxygen saturation), time to cessation of oxygen support.
- The difference between VIS410 + oseltamivir and oseltamivir alone treatment groups in the following endpoints:
 - Peak viral load, viral AUC, duration of viral shedding, and time to resolution of viral load from nasopharyngeal swabs by $TCID_{50}$ and qRT-PCR
 - Time to clinical response defined as resolution of at least 4 of 5 vital signs
 - Afebrile with core temperature $\leq 37.8^\circ C$, without use of antipyretics (oral $\leq 37.2^\circ C$)
 - Oxygen saturation $\geq 95\%$ on room air without support or a return to pre-infection status, if pre-infection status was $< 95\%$
 - Pulse rate $\leq 100/min$
 - Systolic blood pressure ≥ 90 mm/Hg, without vasopressor use
 - Respiratory rate ≤ 24 beats per minute

- Clinical status ordinal scale mean area under curve for Days 1-7 and Days 1-14, using linear numeric scores for the ordinal categories.
- Comparison of clinical status ordinal scale scores for selected individual days (ie, Days 3, 4, 5, and 6)
- Comparison of clinical status ordinal scale scores using modified ordinal scale criteria (ie, pooling of selected severity criteria scores)
- Comparison of discrete ordinal scale parameters, including days of ventilator support, days in intensive care, and duration of hospitalization
- Number of days to resumption of usual activities
- All-cause and attributable mortality rates at Day 14, 28, and 56
- Total number of days in hospital and/or intensive care unit (ICU) from admission to discharge and rate of rehospitalization due to influenza A relapse/complication
- The incidence, severity, and duration of signs and symptoms of influenza-like illness as assessed by the FluPRO Questionnaire (see Appendix 14.1)
- Analysis of time to alleviation of signs and symptoms of influenza in the subset of subjects able to complete the Influenza Patient Reported Outcomes (FluPRO) Questionnaire at baseline and post-dose by Kaplan Meier analysis

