6.3.4 Resumption of Normal Activities

Subjects will complete a visual analog scale (VAS) daily from Day 1 (baseline) until either the subject reports that all usual activities (prior to influenza onset) can be performed or Day 56, whichever comes first. The VAS scale ranges from 0 to 10, where 0 indicates subject is unable to perform usual activities at all, and 10 indicates subject is able to perform all usual activities fully)

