8.4 Subject Diary

A subject diary will be provided upon discharge from the hospital and will record the following:

- Daily oseltamivir dosing to be completed for as long as the subject continues to take oseltamivir
- Daily VAS for assessing resumption of usual activities to be completed up until either the subject reports that all pre-influenza usual activities can be performed or Day 56, whichever comes first
- Daily Influenza Patient Reported Outcomes (FluPRO) Questionnaire to be completed until Day 14, if applicable

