10.5 Handling of Missing Data

Procedures for handling missing data will be defined in the Statistical Analysis Plan, and may include last observation carried forward or an interpolation method.

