10.6.5 Healthcare Resource Utilization

Descriptive statistics will be used to compare the total number of days in the hospital and/or ICU from admission to discharge, number of subjects requiring ICU admission post-randomization, overall number of days in the ICU, number of hours on ventilation, rehospitalization due to influenza A relapse/reinfection, the total number of days of oseltamivir therapy, and the total number of days to resumption of usual activities by treatment group.

Time (number of days) to resumption of usual activities will be determined from the VAS (scale ranged from 0 to 10, where 0 indicates subject is unable to perform any of his/her usual activities prior to influenza onset, and 10 indicates subject is able to fully perform all usual activities).

This evaluation will be performed using the MITT population.

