## 4 GENERAL ANALYSIS DEFINITION

### 4.1 General Considerations

All statistical analyses and summary information are to be generated according to this SAP. Any deviations from this SAP will be documented in the clinical study report (CSR).

These descriptive statistics will be presented for continuous parameters: the number of subjects used in the calculation (n), mean, standard deviation (SD), median, minimum, and maximum values. For PK parameters, the geometric mean and coefficient of variance (CV) will also be presented. All continuous summaries will display the minimum and maximum value with the same number of decimals collected in the data. The median, mean, geometric mean and CV will display 1 additional decimal, and the SD and SE will display 2 additional decimals. For categorical variables, frequencies and percentages will be reported. All percentages will be reported to 1 decimal; all p-values will be reported to 3 decimals.

All temperature measurements will be presented as degrees Celsius. Degrees in Fahrenheit will be converted with this formula:

$$T_C = (T_F - 32) * (5/9),$$

where  $T_C$  is a Celsius temperature and  $T_F$  is a Fahrenheit measurement.

Since this is a phase 2 study rigorous control over type 1 error will not be used; all statistical comparisons will be performed using 2-sided tests at the 0.05 significance level, unless specifically stated otherwise. All null hypotheses will be defined as no treatment difference. All p-values are presented for informational purposes only; there will not be any adjustments for multiple comparisons.

All analyses, summary tables, figures, and data listings will be generated with SAS version 9.4 or higher. Specialized PK software will be used for some PK analyses.

Baseline is defined as the latest non-missing measurement taken prior to study drug administration.

January 17, 2019

All summaries will be by actual visit, no visit windows for analysis will be defined. In general, summaries will be by treatment groups, and will include a combined VIS410 treatment group, in addition to the individual low dose (2000 mg) VIS410, high dose (4000 mg) VIS410, and Placebo treatment groups, unless specified differently. Summaries of disposition, other baseline data, and adverse events will also include an overall column.

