#### **9.2.5 Healthcare resource utilization**

Descriptive statistics will be used to compare the total number of days in the hospital and/or ICU from admission to discharge, number of subjects requiring ICU admission post-randomization, overall number of days in the ICU, number of hours on ventilation, rehospitalization due to influenza A relapse/reinfection, the total number of days of oseltamivir therapy, and the total number of days to resumption of usual activities by treatment group.

Time (number of days) to resumption of usual activities will be determined from the VAS (scale ranged from 0 to 10, where 0 indicates subject is unable to perform any of his/her usual activities prior to influenza onset, and 10 indicates subject is able to fully perform all usual activities). Time to resumption of usual activities will be calculated as the difference between the first day the subject reports a score of 10 and Day 1. If a subject does not report a score of 10 by Day 14, a value of 14 will be used in the analysis. This evaluation will be performed using the MITT population. Additional analyses of VAS scores will reflect summaries of mean VAS scores by study day (up to Day 14), along with change from baseline and percent change from baseline will be generated; p-values will be based on ANOVA using rank transformation of VAS scores. VAS summaries will also be generated in the subsets of subjects with time from onset of symptoms to treatment < 72 hours or ≥ 72 hours. Mean VAS scores by study day along with standard deviations will be presented in figures, overall subjects and in the indicated subsets.

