 Subjects who terminate the study participation early are encouraged to have all follow-up safety assessments done at the time of study termination. All other subjects will return for a final follow-up visit at Day 56 ± 7 days.

 Single nasopharyngeal swab will be obtained from one nostril for influenza A rapid test. This screening test is not necessary if the subject has a prior influenza A positive test by Rapid Antigen Test or with another commercially available test including PCR, FIA, or ELISA within the prior 48 hours of screening.

 Collect all medications taken, including over-the-counter, within 7 days prior to VIS410/placebo administration.

 Randomization will be stratified by presence or absence of positive pressure ventilation (PPV) at baseline to ensure an even distribution across treatment arms.

 Subject diary will be provided upon discharge from the hospital and will record daily oseltamivir dosing (as applicable) and will have a daily VAS for assessing resumption of usual activities until either the subject reports that all usual activities (prior to influenza onset) can be performed or Day 56, whichever comes first. In addition, the Influenza Patient Reported Outcomes (FluPRO) Questionnaire will be provided and completed daily up until Day 14 (if applicable).

 Additional safety assessments may be performed outside of the defined protocol criteria, at the Investigator's discretion.

 Single 12-lead ECG will be performed after a 5-minute rest in supine position.

 To be repeated only if screening and baseline visits are more than 24 hours apart.

January 17, 2019

- 
-  Vital signs should be measured after 5 minutes of rest in a supine position and include heart rate, respiratory rate, and blood pressure. During hospitalization, vital signs will be measured at the end of the infusion on Day 1 and then BID (preferably at the same time each day) up until Day 14 or discharge from the hospital if this occurs prior to Day 14.
-  Baseline SpO2 on room air to be documented, if available. Once randomized, SpO2 to be measured using pulse oximetry 3 times daily (approximately every 8 hours) at approximately the same time each day until stable. Stable SpO2 is defined as two consecutive SpO2 values of > 92% on room air that are at least 8 hours apart.

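### SAP 9.2.5 records 14 days to resumption of usual activities for anyone without a VAS of 10 by Day 14, although the VAS is collected to Day 56, and SAP 16.1 does not list this cap

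*SAP*

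**What the plan says.** **Endpoint.** Protocol 3.2 lists "Number of days to resumption of usual activities" as a secondary endpoint. Protocol 10.6.5 plans a descriptive comparison of "the total number of days to resumption of usual activities by treatment group", taken from the VAS, and states no Day 14 limit.

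**Collection.** Protocol 6.3.4 has subjects complete the VAS daily from Day 1 "until either the subject reports that all usual activities (prior to influenza onset) can be performed or Day 56, whichever comes first". The diary in Protocol 8.4 runs until "all pre-influenza usual activities can be performed or Day 56, whichever comes first". The SAP repeats this in footnote 6 of its schedule (16.2): the diary "will have a daily VAS for assessing resumption of usual activities until either the subject reports that all usual activities" can be performed, or Day 56.

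**SAP rule.** SAP 9.2.5 takes the first day with a score of 10, subtracts Day 1, and adds: "If a subject does not report a score of 10 by Day 14, a value of 14 will be used in the analysis". Within 9.2.5 there is no censoring, no flag for capped values and no use of later scores for this endpoint.

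**Related text.** Protocol 10.5 leaves missing-data methods to the SAP, which "may include last observation carried forward or an interpolation method". SAP 16.1 lists four changes to the protocol's analyses: the per-protocol population, the MITT definition, the QTcF categories and the five-point scale. The cap is not among them, and the version 2.0 change log mentions only mean VAS scores for 9.2.5.

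**The concern.** The rule replaces recorded durations with a shorter one. A subject whose diary shows the first 10 on Day 28 took 27 days but is entered as 14. So is a subject who dies on Day 5, one who drops out and one who never resumes.

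The study is meant to find candidate endpoints for Phase 3 (SAP 2.2). The protocol's efficacy section also names time to resumption as an outcome against which peak viral load and ventilator days may be correlated. Giving one value to everyone who has not resumed by Day 14 removes the variation among the slowest recoverers, shortens the reported means and compresses differences between arms. A reader of the report would find no entry in SAP 16.1 to warn of this.

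**Working it through.** **1. Apply the rule to possible resumption days** (duration = day − 1).

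| First VAS of 10 | True duration | Value under SAP 9.2.5 | Shortfall |
|---|---|---|---|
| Day 14 | 13 | 13 | 0 |
| Day 15 | 14 | 14 | 0 (by coincidence) |
| Day 16 | 15 | 14 | 1 |
| Day 28 | 27 | 14 | 13 |
| Day 42 | 41 | 14 | 27 |
| Day 56 | 55 | 14 | 41 |

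Values are wrong from Day 16 onward. This step needs no assumption.

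**2. Look for a clause that covers it.** Protocol 10.5 concerns missing data, but scores on Days 15 to 56 are recorded. SAP 9.2.6 also uses 14 days for FluPRO, but FluPRO collection ends at Day 14, capped values are listed as >14, and Kaplan-Meier estimates are added. SAP 9.2.3 and 9.2.4 use Kaplan-Meier with censoring for clinical response and ventilator support. Resumption has none of these safeguards. The outputs in SAP 16.6 place it only in the resource-utilization summary (Table 14.2.5.1).

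**3. Illustrate the size.** The documents give no resumption times, so the following are assumptions: exponential times, hazard ratio 1.4 for VIS410, no deaths or dropout, and placebo medians of 7, 14, 21 and 28 days. The effect either persists or stops at 13 days (Day 14 − Day 1).

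- Placebo hazard λ₀ = ln 2 / median; VIS410 hazard λ₁ = 1.4 λ₀.
- Mean to horizon T = (1 − e^(−λT))/λ, with T = 14 for the cap and T = 55 for Day 56.
- Share assigned 14 = S(13). Share with a recorded resumption that is shortened = S(14) − S(55).

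Example, placebo median 21: λ₀ = 0.0330, λ₁ = 0.0462.

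- Capped: placebo (1 − 0.630)/0.0330 = 11.2; VIS410 (1 − 0.524)/0.0462 = 10.3; difference 0.9.
- To Day 56: placebo (1 − 0.163)/0.0330 = 25.37; VIS410, effect persisting, (1 − 0.079)/0.0462 = 19.94; difference 5.4.
- To Day 56, effect ending at Day 14: VIS410 (1 − 0.548)/0.0462 + 0.548 × (1 − 0.25)/0.0330 = 9.78 + 12.45 = 22.2; difference 3.1.
- Placebo mean understated by 25.4 − 11.2 = 14.2 days.

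All cases (days; shares are placebo/VIS410):

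| Placebo median | Placebo mean understated | Mean difference, capped | To Day 56, persists | To Day 56, ends at Day 14 | Assigned 14 | Shortened, persists | Shortened, ends at Day 14 |
|---|---|---|---|---|---|---|---|
| 7 | 2.5 | 1.4 | 2.8 | 2.4 | 28%/16% | 25%/14% | 25%/15% |
| 14 | 8.8 | 1.1 | 4.8 | 3.1 | 53%/41% | 43%/36% | 43%/34% |
| 21 | 14.2 | 0.9 | 5.4 | 3.1 | 65%/55% | 47%/44% | 47%/39% |
| 28 | 18.2 | 0.7 | 5.5 | 2.9 | 72%/64% | 45%/47% | 45%/40% |

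Medians in whole days are right at 7/5 and 14/10. With a placebo median of 21, both arms report 14 instead of 21/15 (persists) or 21/16 (ends at Day 14).

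Faster recovery shrinks the problem. By the same formulas, a placebo median of 4 days gives an understatement of 0.5 days with 11%/4% assigned 14; a median of 5 gives 1.0 day with 16%/8%.

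**The case against.** A mean truncated at 14 days is a recognised kind of summary. It is fully specified, needs no assumption about diaries that stop after Day 14, and matches the horizon of the ordinal scale and FluPRO. Visits after Day 14 are only at Days 28 and 56, so later diaries may be less complete. That argument supports keeping the measure with a label. It does not support presenting it as the number of days to resumption, because SAP 9.2.5 never calls it restricted.

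Longer follow-up also does not reliably gain power. In simulations of 40 vs 80 subjects (2000 trials per cell, Monte Carlo error about 1 point) with placebo medians of 7, 14 and 21, a rank test on capped values had 28/23/18%, against 38/40/36% for a log-rank test to Day 56, if the effect persists. If it ends at Day 14 the order reverses: 30/22/18% against 25/14/12%. This stands, and no power gain is claimed. Neither test is planned for this endpoint, and SAP 4.1 says "All p-values are presented for informational purposes only".

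Protocol 10.0 leaves further statistical detail to the SAP, so the cap may be read as detail and not as a change. The table shells are separate and could carry a footnote. Neither point restores the overwritten durations.

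Finally, the sizes are hypothetical and could be small if most subjects resume within a week. That stands too.

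**Conclusion.** The concern holds. The SAP discards recorded VAS data and enters a wrong duration for every subject whose first 10 falls on Days 16 to 56. It merges these subjects with deaths, dropouts and non-resumers, and SAP 16.1 does not disclose it. That part follows from the text alone.

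The size is not known. Under the stated assumptions the placebo mean is understated by 2.5 to 18.2 days for placebo medians of 7 to 28, and by 1 day or less for medians of 4 or 5. The capped mean difference is smaller than the difference to Day 56 in every tabulated case, whether or not the effect lasts beyond Day 14. The assumption of no deaths or dropout means these figures do not test how such subjects should be handled.

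This is a descriptive secondary endpoint in an exploratory trial. The primary analysis and the sample size are untouched. It should be corrected, but it does not threaten the trial's main result.

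**What to change.** In SAP 9.2.5 replace the value-of-14 rule with:

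> Time from Day 1 to the first VAS score of 10 will use all VAS data to Day 56. Kaplan-Meier median and quartiles will be reported by arm and for combined VIS410, with the proportions resumed by Days 14, 28 and 56. Survivors without a score of 10 are censored at their last VAS. Subjects who die before any score of 10 stay at risk to Day 56 as never resumed.

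The death rule differs from the censoring in SAP 9.2.3 and 9.2.4 and should be stated explicitly: censoring a death would treat that subject as still able to resume.

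Keep the value-of-14 measure only as a supplementary summary labelled as restricted to 14 days. As a check on incomplete diaries, repeat the proportions counting survivors who stop the diary before a 10 as not resumed. Add the change to SAP 16.1. A log-rank p-value is optional and informational.

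The cost is SAP wording, one descriptive table and one line in 16.1, with no new data collection. The drawback is that censoring at the last VAS assumes those subjects go on to resume at the same rate as the others. The labelled 14-day summary and the not-resumed check show how much that matters.

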### 3.3 Exploratory Endpoints

- Average VAS scores at each visit
- Pharmacokinetics of VIS410 from nasopharyngeal secretions
- VIS410 concentrations in tracheal aspirates
- The difference in viral load between VIS410 + oseltamivir and oseltamivir alone treatment groups in tracheal aspirates of subjects on mechanical ventilation
- Titer of anti-influenza A antibodies by hemagglutinin inhibition assay (HAI) in serum
- Correlations between serum and/or nasopharyngeal PK with viral load, clinical symptoms, presence of ADAs, safety, and additional endpoints

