## 4.2 Missing Data Conventions

Partial and missing AE and concomitant medication dates will be imputed with maximum conservatism. If the onset date is missing or partial, the date will be compared as far as possible with the date of first dose of study medication. If no month is present and it is in the same year as the date of first treatment, or the year and month are the same as the first treatment date, the onset date will be imputed as the date of first treatment. Otherwise it will be imputed as 01 January in the available year, or the first day of the month and year available. End dates will be imputed as 31 December in the available year, or the last day of the available month and year collected. Partial dates will be presented in listings, along with classifications of TEAE for AEs or Prior/Concomitant/Both for medications.

Missing data will generally be left as missing, except for partial and missing AE and concomitant medication dates. Special cases, e.g. below the limit of quantification, will be described in the sections that describe the specific parameter's analysis.

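### Daily VAS collection stops at full recovery, so the mean VAS by study day in SAP 9.2.5 drops recovered subjects and later-day comparisons lean against the faster-recovering arm

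*SAP*

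**What the plan says.** Protocol 6.3.4 collects the VAS "daily from Day 1 (baseline) until either the subject reports that all usual activities (prior to influenza onset) can be performed or Day 56". Protocol 8.4 repeats the rule for the diary: "Daily VAS for assessing resumption of usual activities to be completed up until either the subject reports that all pre-influenza usual activities can be performed". Footnote 6 of the protocol's Table 1 agrees, and so does the SAP's own copy of the schedule in Appendix 16.2: the diary "will have a daily VAS for assessing resumption of usual activities until either the subject reports that all usual activities" can be performed. SAP 9.2.5 fixes the score for that state: "10 indicates subject is able to fully perform all usual activities".

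The same section then specifies "summaries of mean VAS scores by study day (up to Day 14", change and percent change from baseline, p-values from ANOVA on rank-transformed scores, the same summaries for subjects treated under 72 hours and at 72 hours or more from symptom onset, and figures. SAP 3.3 lists the endpoint as "Average VAS scores at each visit".

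On missing values, SAP 4.2 says "Missing data will generally be left as missing" and leaves special cases to each parameter's own section. The only substitution in 9.2.5 concerns time to resumption, which is set to 14 when no score of 10 is reported by Day 14. Nothing covers the daily scores after a 10.

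**The concern.** The missing scores are created by the protocol, and they are missing because the subject reached the best possible outcome. From the day after the first 10, each daily mean covers only subjects who have not yet recovered, plus those recovering that day. A treatment that speeds recovery takes its successes out of its own mean.

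The SAP sets explicit rules elsewhere: achieved criteria carry forward for clinical response (9.2.3), death carries forward on the ordinal scale (9.1), and viral load has a last-observation-carried-forward analysis (9.2.8). FluPRO is collected daily to Day 14 with no stop at recovery (9.2.6). The VAS means were added in SAP version 2.0 without a matching rule.

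At stake is an understated VAS effect in Table 14.2.5.2 and Figure 14.2.5.2, in a trial whose p-values are meant to indicate how sensitive its endpoints are.

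**Working it through.** The documents state no VAS mean, recovery rate or power, so there is no figure to reproduce. Every input below is an assumption except the collection rule, the 0 to 10 scale, 40 subjects per arm and the two-sided 0.05 level.

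**Arithmetic.** Let p be the share with a first 10 before a given day, and m the mean of everyone else.
- Recovered subjects counted as 10: mean = 10p + m(1 − p).
- Recovered subjects missing, as planned: mean = m.
- With p = 50% vs 25% and m = 6 in both arms, counting them gives 0.50×10 + 0.50×6 = 8.0 and 0.25×10 + 0.75×6 = 7.0, a difference of 1.0. The planned analysis gives 6.0 vs 6.0, a difference of 0.
- Over m = 5 to 7 and recovered shares of 30/20%, 50/25% and 60/40%, the lost difference runs from 0.3 to 1.25 points.

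**Simulation A.** 40 per arm, 4000 runs; log-normal day of first 10; roughly linear rise from a baseline of 0 to 3; two-group rank ANOVA. Each cell gives the result with 10 carried forward, then as planned.

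| Median day of first 10 (log-SD) | Day 7 difference | Day 10 difference | Day 14 difference | Day 10 share with p<0.05 |
|---|---|---|---|---|
| 8 vs 12 (0.6) | 1.49, 1.00 | 1.18, 0.77 | 0.75, 0.59 | 0.74, 0.22 |
| 10 vs 14 (0.6) | 1.25, 0.87 | 1.13, 0.72 | 0.82, 0.56 | 0.60, 0.22 |
| 8 vs 12 (0.9) | 1.14, 0.67 | 0.98, 0.56 | 0.75, 0.50 | 0.41, 0.12 |
| 14 vs 20 (0.6) | 1.18, 0.93 | 1.32, 0.90 | 1.20, 0.76 | 0.66, 0.40 |

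Day 10 reduction by row: 0.41/1.18 = 35%, 0.41/1.13 = 36%, 0.42/0.98 = 43%, 0.42/1.32 = 32%. In the first row about 17 of 40 vs 27 of 40 subjects still contribute at Day 10, and about 8 vs 18 at Day 14.

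**Simulation B.** A different model: 80 pooled VIS410 vs 40 placebo; score = individual rate × days since Day 1, rounded and held to 0–10; log-normal rate with median 0.8 per day and log-SD 0.5; noise SD 0.7; rate 1.3 times higher on VIS410. At Day 10, 60% vs 78% contribute, the mean difference falls from 1.10 to 0.73, and rank-test power falls from 67% to 30%. At Day 14 power falls from 56% to 14%. The loss in the mean difference is about 0.06 at Day 5, 0.25 at Day 7, 0.36 at Day 10 and 0.19 at Day 14.

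**The case against.** The strongest reply is that this is one exploratory summary. Mean VAS is exploratory in SAP 2.4.3 and 3.3, and SAP 4.1 calls all p-values informational. The secondary VAS endpoint, time to resumption, uses the first 10 and loses nothing this way, so faster recovery is still measured in the same section. SAP 4.1 also requires n with every continuous summary, so the shrinking denominator would be visible. All of this stands and limits the consequence. Showing n, however, does not correct the mean, the test or the plotted curve.

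A reader might infer more than the documents support on four points:
- **The bias grows every day.** In simulation B, and in three of the four scenarios in A, the lost mean difference peaks around Day 7 to Day 10 and then shrinks; only in the slowest-recovery scenario is it still rising at Day 14 (0.42 at Day 10, 0.44 at Day 14). Power does keep falling relative to the carried-forward analysis, partly because n falls.
- **The sign will reverse.** It can. With 50% vs 30% recovered and the rest averaging 5.5 vs 6.0, the means counting recovered subjects are 7.75 vs 7.2 (+0.55), while the planned analysis shows −0.5. But the 5.5 is chosen for the example, and the expected difference stayed in favour of the faster arm on every simulated day.
- **False positives rise.** With no treatment effect in simulation B, the error rate stayed near 5%.
- **A working endpoint would be discarded.** SAP 2.2 draws Phase 3 candidates from the primary and secondary endpoints. The protocol synopsis does also mention exploratory p-values as a basis for endpoint choice, so the risk is not nil, but the unaffected time-to-resumption endpoint makes it small.

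There is also a fair objection to the obvious remedy. Filling every later day with 10 could score a readmitted subject as fully active. Relapse is partly recorded: the daily ordinal scale separates full from partial resumption through Day 14 (SAP 9.1), and rehospitalization and its reason are captured to the last visit (protocol 6.3.5). Nor does any document give death a VAS value, so assigning it 0 would be an arbitrary choice. Both points shape the fix.

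**Conclusion.** The point holds. Taken together, the stopping rule, the daily means and the missing-data convention remove recovered subjects from the day after their first 10, and 9.2.5 does not correct for it. Followed literally, the plan gives a biased comparison.

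The direction, against the faster-recovering arm, follows from the design, provided the arms differ in the share recovered and recovered subjects would have continued to score near 10. The size does not follow from the documents. On assumed inputs the Day 10 difference shrinks by about a third (32% to 43%), with a large loss of power. The effect is clear from about Day 7, and earlier where recovery is early. The simulated tests compare two groups, whereas the trial has three arms, so the power figures show scale only.

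The primary endpoint and time to resumption of usual activities are untouched. The point is worth correcting because the correction is cheap and the figure would mislead even without a p-value.

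**What to change.** Add to SAP 9.2.5: *After a subject's first VAS score of 10, each later day through Day 14 without a recorded score is assigned 10, unless that day's ordinal-scale or rehospitalization record shows the subject in hospital, at partial resumption only, or dead; such a day is not filled with 10.* State in advance how days after death are handled, for example worst rank in the rank analysis, since leaving them missing removes poor outcomes from the mean. State too that other missing days stay missing.

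Apply the rule to Table 14.2.5.2 (means, change and percent change), the rank tests, the 72-hour subsets and Figure 14.2.5.2. Keep the observed-case version as a sensitivity analysis, with the already planned n shown by day and arm.

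The cost is a short SAP addition and a programming step that merges the VAS with the ordinal and rehospitalization records. No new data are needed. The downside is that a relapse captured by neither record would be scored as 10.
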